**Data collection for all ePRO measures will be dependent on ePRO device and software availability.**

#### **8.2.2.1 Leicester Cough Questionnaire**

Participants will be asked to complete the 19-item LCQ to assess the impact of their cough severity on physical, social and psychological functioning.

#### **8.2.2.2 Cough Severity Diary**

Participants will be asked to record their cough frequency, intensity, and disruption due to cough using the 7-item CSD. Participants will rate each item using an 11-point scale ranging from 0 to 10 with higher scores indicating greater severity.

Participants will complete the CSD at approximately the same time daily, beginning at Visit 1 until Visit 9 (with a minimum requirement of 7 days of completion prior to first dose of study intervention/Randomization).

During the Extension study period, completion of the CSD will be required daily, at approximately the same time for a 1 week period, beginning 1 week prior to Visit 11 and beginning 1 week prior to Visit 13. Participants should be contacted (eg, by telephone or text) during the Extension study period to remind them to complete the CSD during these weeks.

### **8.2.2.3 Cough Severity Visual Analog Scale**

Participants will be asked to rate the severity of their cough over the past 24 hours using a 100 mm Cough Severity VAS single-item questionnaire with the response ranging from 0 (“No Cough”) to 100 (“Extremely Severe Cough”).

Participants will complete the Cough Severity VAS at approximately the same time daily, beginning at Visit 1 until Visit 9 (with a minimum requirement of 7 days of completion prior to first dose of study intervention/Randomization).

In order to confirm participant eligibility, study site staff will be required to review/confirm, the:

- Participant met the Screening Cough Severity VAS criteria from the measurement done on the day of Visit 1 (or from the next day, if the evening measure was missed).
- Participant met the Baseline Cough Severity VAS criteria from the measurement done on the day prior to Visit 2 prior to conducting any other Visit 2 procedures (or from the morning of Visit 2, prior to conducting any Visit 2 procedures, if the evening measure was missed).

A score of  $\geq 40$  mm on the Cough Severity VAS, at both the Screening and Baseline visits is required for randomization into the study.

During the Extension study period, completion of the Cough Severity VAS will be required daily, at approximately the same time for a 1 week period beginning 1 week prior to Visit 11 and beginning 1 week prior to Visit 13. Participants should be contacted (eg, by telephone or text) during the Extension study period to remind them to complete the Cough Severity VAS during these weeks.

### **8.2.2.4 12-item Short Form Survey**

The SF-12 is a validated, 12-item questionnaire designed to assess general health-related quality of life. It is a widely used instrument that has been shown to be responsive to changes in disease severity following intervention. The SF-12 is scored such that a total score and 8 domain scores can be calculated with higher scores indicating better functioning: Physical Functioning, Role-Physical, Role-Emotional, Bodily Pain, General Health, Social

Functioning, Mental Health, and Vitality. Data obtained from the SF-12 will be used in health economic analyses.

### **8.2.2.5 Work Productivity and Activity Impairment Questionnaire**

The WPAI questionnaire yields four types of scores as follows: (1) absenteeism (work time missed); (2) presenteeism (impairment at work / reduced on-the-job effectiveness); (3) work productivity loss (overall work impairment / absenteeism plus presenteeism); and (4) activity impairment. The WPAI outcomes are expressed as impairment percentages, with higher numbers indicating greater impairment and less productivity, ie, worse outcomes.

Participants will be asked to indicate if they are currently employed and to respond to the following questions referring to “the past 7 days”: work hours missed due to health problems, work hours missed for other reasons, hours actually worked, the degree to which their health has affected productivity while working, and the degree to which their health affected productivity in regular unpaid activities.

### **8.2.2.6 EuroQoL 5L Dimensions Questionnaire**

The EQ5D-5L is a standardized instrument for measuring generic health status used for estimating preference weights for that health status. By combining the weight with time, quality adjusted life years can be computed. The EQ5D-5L descriptive system comprises the following 5 dimensions: mobility, self-care, usual activities, pain/discomfort and anxiety/depression. Each dimension has 5 levels and the participant will be asked to indicate their health state using a 5-level rating scale. The EQ VAS records the participant’s self-rated health on a vertical VAS where the endpoints are labeled ‘best imaginable health state’ and “worst imaginable health state”. This information can be used as a quantitative measure of health outcome as judged by the individual participant.

### **8.2.2.7 Patient Global Impression of Change Questionnaire**

Participants will be asked to rate the change in their chronic cough compared to the start of the study using the PGIC with response options ranging from “very much improved” to “very much worse”.

### **8.2.2.8 Hull Airway Reflux Questionnaire**

Unlike the other cough questionnaires used in this study (ie, LCQ, CSD, and Cough Severity VAS), the HARQ was designed as an aid to diagnosis rather than assess quality of life impacts or cough severity. The HARQ has demonstrated good psychometric properties and no redundant items. The HARQ consists of 14 questions with responses on a numeric scale from 0 to 5. A score of “0” means that no problems are caused by the cough symptom and “5” means severe/frequent problems. The HARQ will be used to more completely characterize the patient population.

### **8.3 Safety Assessments**

Details regarding specific safety procedures/assessments to be performed in this study are provided. The total amount of blood/tissue to be drawn/collected over the course of the study (from prestudy to poststudy visits), including approximate blood/tissue volumes drawn/collected by visit and by sample type per participant, can be found in Section 8.

Planned timepoints for all safety assessments are provided in the SoA.

#### **8.3.1 Chest Radiography/Computed Tomography Thorax Scan**

A chest radiograph or computer tomography scan of the thorax should be performed locally for participants, at Screening, if this has not been done within the last 5 years and after the onset of chronic cough. The chest radiograph or computer tomography scan of the thorax should not demonstrate any abnormality considered to be significantly contributing to the chronic cough or any other clinically significant lung disease in the opinion of the principal investigator (or sub-investigator, see inclusion criterion 1, Section 5.1).

#### **8.3.2 Physical Examinations**

A complete physical examination will include assessments of the following: general appearance; skin and lymphatic; eyes, ears, nose, throat; cardiovascular system; respiratory system; abdomen/gastrointestinal system; urological system; musculoskeletal and neurological systems. Other body systems may be examined.

Any clinically significant abnormalities in physical examinations noted after Visit 1 will be recorded as AEs in the eCRF.

A brief directed physical exam may be performed at any study site visit that does not already include a physical exam if deemed necessary by the investigator due to signs/symptoms. A physical exam (complete or directed) can be performed at any unscheduled visit if deemed necessary by the investigator.

Investigators should pay special attention to clinical signs related to previous serious illnesses.

#### **8.3.3 Vital Signs and Weight and Height Measurements**

Vital sign measurements, including systolic blood pressure (mm Hg), diastolic blood pressure (mm Hg), heart rate (beats per minute), respiratory rate (breaths per minute), and body temperature (in centigrade) will be collected as outlined in the SoA. All blood pressure measurements should be performed on the same arm, preferably by the same person.

Height (cm) and weight (kg) will also be collected as per the SoA.

Any clinically significant abnormalities in vital signs noted after Visit 1 will be recorded as AEs in the eCRF.

### 8.3.4 Electrocardiograms

A 12-lead ECG will be performed at Screening using local standard procedures. Clinically significant abnormal findings should be recorded in the AE eCRF.

### 8.3.5 Spirometry

A spirometry assessment will be performed locally at Screening using a calibrated spirometer. Assessments will include FEV1, FVC, and FEV1/FVC ratio.

Spirometry should be performed in accordance with guidelines established by the ATS/ERS (Available from: <http://www.thoracic.org/statements/>). For safety reasons, spirometry should be performed with the participant sitting, using a chair with arms and without wheels; however, if necessary to undertake the testing with the participant standing or in another position, this should be noted in the participant's study file.

Spirometry performed within the past year of screening is acceptable if the investigator confirms that spirometry was done during a period where the participant was clinically stable (eg, not during an upper respiratory infection).

### 8.3.6 Clinical Safety Laboratory Assessments

- Refer to Appendix 2 for the list of clinical laboratory tests to be performed and to the SoA for the timing and frequency.
- The investigator or medically qualified designee (consistent with local requirements) must review the laboratory report, document this review, and record any clinically relevant changes occurring during the study in the AE section of the case report form (CRF). The laboratory reports must be filed with the source documents. Clinically significant abnormal laboratory findings are those which are not associated with the underlying disease, unless judged by the investigator to be more severe than expected for the participant's condition.
- All protocol-required laboratory assessments, as defined in Appendix 2, must be conducted in accordance with the laboratory manual and the SoA.
- If laboratory values from nonprotocol specified laboratory assessments performed at the institution's local laboratory require a change in study participant management or are considered clinically significant by the investigator (eg, SAE or AE or dose modification), then the results must be recorded in the appropriate CRF (eg, SLAB).
- For any laboratory tests with values considered clinically significantly abnormal during participation in the study or within 7 days after the last dose of study intervention, every attempt should be made to perform repeat assessments until the values return to normal or baseline or if a new baseline is established as determined by the investigator.

### 8.3.7 Renal and Urological Safety Assessments

Safety assessments will be performed in all participants in order to monitor renal and urological safety during the course of the study. Participants will be monitored for hematuria using urinary dipstick (performed at the study site) and urinary crystals and hematuria through urinalysis (performed at the central laboratory). Dipstick and urinalyses (including microscopy) will be collected as outlined in the SoA.

If during screening, a participant has crystalluria and/or unexplained hematuria (defined as, for example, participants without a history of recent menses, urinary tract infection, or recent procedure/instrumentation that would explain the hematuria; Note: Any other explanation for hematuria finding must be reviewed with the Sponsor.), the investigator should:

- Review and confirm if the finding is a new finding or a previously documented finding.
- Evaluate the participant's medical history to identify conditions (ie, prior renal disease, prior history of kidney stones, medications, gastrointestinal conditions) and make a clinical determination if the participant is at high or low risk of potential complications/worsening due to an associated renal/urinary condition or its treatment, or requires a change in therapy for that condition that may interfere with interpretation of safety data collected during the study.
- If high risk, the participant should not be enrolled and should be considered for further evaluation.
- If low risk, the participant may continue with screening.

If after randomization, the participant has confirmed, unexplained hematuria and/or urinary crystals per the central laboratory, an additional urine sample will need to be collected. One half of the sample will be sent to the central laboratory for reconfirmation of unexplained hematuria and/or urinary crystals. The other half of the sample will be collected via a specialized filter and shipped to Sponsor or designee and assessed for the presence of MK-7264 urinary crystals via Raman spectroscopy. Raman spectroscopy is sensitive to the chemical structure of the molecule and MK-7264 has a unique chemical structure compared to common urinary crystals. See vendor's site manual for further procedural details.

If a participant has confirmed MK-7264 urinary crystals, the Sponsor will inform the investigator and require discontinuation of the participant from study intervention with the recommendation to follow-up at approximately 2-week intervals with additional specialized urine analyses performed until resolution of the MK-7264 urinary crystals. Once a participant has confirmed MK-7264 crystals, it will be known that the participant was receiving MK-7264 (formal unblinding should not be performed [see Section 8.1.11]).

## **8.4 Adverse Events (AEs), Serious Adverse Events (SAEs), and Other Reportable Safety Events**

The definitions of an AE or SAE, as well as the method of recording, evaluating, and assessing causality of AE and SAE and the procedures for completing and transmitting AE, SAE, and other reportable safety event reports can be found in Appendix 3.

Adverse events, SAEs, and other reportable safety events will be reported by the participant (or, when appropriate, by a caregiver, surrogate, or the participant's legally authorized representative).

The investigator and any designees are responsible for detecting, documenting, and reporting events that meet the definition of an AE or SAE as well as other reportable safety events. Investigators remain responsible for following up AE, SAEs, and other reportable safety events for outcome according to Section 8.4.3.

The investigator, who is a qualified physician, will assess events that meet the definition of an AE or SAE as well as other reportable safety events with respect to seriousness, intensity/toxicity and causality.

### **8.4.1 Time Period and Frequency for Collecting AE, SAE, and Other Reportable Safety Event Information**

All AEs, SAEs, and other reportable safety events that occur after the consent form is signed but before treatment allocation/randomization must be reported by the investigator if the participant is receiving placebo run-in or other run-in treatment, if the event cause the participant to be excluded from the study, or is the result of a protocol-specified intervention, including but not limited to washout or discontinuation of usual therapy, diet, or a procedure.

From the time of treatment allocation/randomization through last study-related intervention safety follow-up telephone call, all AEs, SAEs and other reportable safety events must be reported by the investigator; however, for those participants who discontinued from the study intervention but continuing to be monitored only the adverse events and other reportable safety events as shown in [Table 3](#) need to be reported from completion of the safety follow-up telephone call/visit following cessation of intervention to the last study-related off-intervention telephone call/visit.

Additionally, any SAE brought to the attention of an investigator at any time outside of the time period specified in the previous paragraph must be reported immediately to the Sponsor if the event is considered drug-related.

Investigators are not obligated to actively seek AE or SAE or other reportable safety events in former study participants. However, if the investigator learns of any SAE, including a death, at any time after a participant has been discharged from the study, and he/she considers the event to be reasonably related to the study intervention or study participation, the investigator must promptly notify the Sponsor.

All initial and follow-up AEs, SAEs, and other reportable safety events will be recorded and reported to the Sponsor or designee within the time frames as indicated in [Table 3](#).

Table 3 Reporting Time Periods and Time Frames for Adverse Events and Other Reportable Safety Events

Type of Event	Reporting Time Period: Consent to Randomization/ Allocation	Reporting Time Period: Randomization/ Allocation through Protocol-specified Follow-up Period	Reporting Time Period: After the Protocol-specified Follow-up Period	Timeframe to Report Event and Follow-up Information to Sponsor:
Non-serious Adverse Event (NSAE)	Report if: - due to protocol-specified intervention - causes exclusion - participant is receiving placebo run-in or other run-in treatment	Report all	Not required	Per data entry guidelines
Serious Adverse Event (SAE)	Report if: - due to protocol-specified intervention - causes exclusion - participant is receiving placebo run-in or other run-in treatment	Report all	Report if: - drug/vaccine related (Follow ongoing to outcome)	Within 24 hours of learning of event
Pregnancy/Lactation Exposure	Report if: - due to intervention - causes exclusion	Report all a	Previously reported – Follow to completion/termination ; report outcome	Within 24 hours of learning of event
Event of Clinical Interest (require regulatory reporting)	Report if: - due to intervention - causes exclusion	Report a - Potential DILI - Require regulatory reporting	Not required	Within 24 hours of learning of event
Event of Clinical Interest (Do not require regulatory reporting)	Report if: - due to intervention - causes exclusion	Report a - non-DILI ECIs and those not requiring regulatory reporting	Not required	Within 5 calendar days of learning of event
Cancer	Report if: - due to intervention - causes exclusion	Report all	Not required	Within 5 calendar days of learning of event

Type of Event	Reporting Time Period: Consent to Randomization/ Allocation	Reporting Time Period: Randomization/ Allocation through Protocol-specified Follow-up Period	Reporting Time Period: After the Protocol-specified Follow-up Period	Timeframe to Report Event and Follow-up Information to Sponsor:
Overdose	Report if: - receiving placebo run-in or other run-in medication	Report all a	Not required	Within 5 calendar days of learning of event

DILI = drug-induced liver injury; ECI = event of clinical interest

a Participants who discontinue study intervention and are continuing to be monitored in the study do not require the reporting of ECIs, pregnancy/lactation exposure, and overdose. Previously reported pregnancies/lactations exposure need to be followed for completion/termination; report outcome.

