## Female Participants

5. A female participant is eligible to participate if she is not pregnant (Appendix 5), not breastfeeding, and at least 1 of the following conditions applies:
  - a. Not a woman of childbearing potential (WOCBP) as defined in Appendix 5.

OR

- b. A WOCBP who agrees to follow the contraceptive guidance in Appendix 5 from the time of signing the informed consent through at least 14 days after the last dose of study intervention.

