#### **8.4.5 Pregnancy and Exposure During Breastfeeding**

Although pregnancy and infant exposure during breastfeeding are not considered AEs, any pregnancy or infant exposure during breastfeeding in a participant (spontaneously reported to the investigator or their designee) that occurs during the study are reportable to the Sponsor.

All reported pregnancies must be followed to the completion/termination of the pregnancy. Pregnancy outcomes of spontaneous abortion, missed abortion, benign hydatidiform mole, blighted ovum, fetal death, intrauterine death, miscarriage, and stillbirth must be reported as serious events (Important Medical Events). If the pregnancy continues to term, the outcome (health of infant) must also be reported.

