### **8.4.1 Time Period and Frequency for Collecting AE, SAE, and Other Reportable Safety Event Information**

Between Visit 13 and Visit 14:

For all study participants, including those entering the Off-treatment Durability Study Period, see Section 8.4.1 of the main protocol for information regarding collection of AEs, SAEs, and Other Reportable Safety Event Information through the 14-day safety follow-up contact (Visit 14).

After Visit 14:

For participants in the Off-treatment Durability Study Period, after Visit 14, the following must be reported to the Sponsor within 24 hours of learning of the event:

- Any drug-related SAEs or SAEs considered to be study participation related and brought to the attention of the investigator
- Any drug-related NSAEs brought to the attention of the investigator during the time the participant is active in the Off-treatment Durability Study Period
- Any pregnancy that is brought to the attention of the investigator during the time the participant is active in the Off-treatment Durability Study Period. The pregnancy must be followed to completion/termination. If the pregnancy continues to term, the outcome (health of the infant) must also be reported.

If the investigator elects to submit AEs for non-Merck products, they should be reported to the Marketing Authorization Holder (MAH) for that product or to the health authority according to the institution's policy or local laws and regulations.

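### Table 3 footnote a drops pregnancy and lactation reporting after the safety call for participants who stop drug but stay in the study, in conflict with Section 8.4.5

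*Combined protocol and SAP*

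**What the plan says.** Section 8.4.1 sets full reporting first: "From the time of treatment allocation/randomization through last study-related intervention safety follow-up telephone call, all AEs, SAEs and other reportable safety events must be reported". The same sentence then narrows this for participants who have stopped study intervention but are still monitored. For them, Table 3 alone decides which events "need to be reported from completion of the safety follow-up telephone call/visit following cessation of intervention to the last study-related off-intervention telephone call/visit".

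In Table 3, footnote a is attached to the pregnancy/lactation, ECI and overdose rows, in the column running from randomisation through the follow-up period. It says that participants off study intervention and "continuing to be monitored in the study do not require the reporting of ECIs, pregnancy/lactation exposure, and overdose". It adds: "Previously reported pregnancies/lactations exposure need to be followed for completion/termination; report outcome". The footnote gives no start time. The rows for non-serious and serious adverse events do not carry it.

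Under Section 8.4.5, a spontaneously reported pregnancy or breastfeeding exposure in a participant "that occurs during the study are reportable to the Sponsor". No exception is made for participants off drug.

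Three other places bear on the point:

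- Section 5.1 requires women of childbearing potential to follow the contraceptive guidance "through at least 14 days after the last dose of study intervention".
- Section 8.10.6 places the safety call about 14 days (+7) after the last dose, and has it repeated if it was made before Day 14.
- Appendix 7 (its Section 8.4.1) requires the following to be reported within 24 hours after Visit 14 in the Off-treatment Durability Study Period: "Any pregnancy that is brought to the attention of the investigator during the time the participant is active" in that period.

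**The concern.** A participant who stops drug early is still in the study: Sections 7.1 and 8.10.5 intend contact at every remaining visit. If she tells the site of a pregnancy after her safety call, Section 8.4.5 has the site report it and footnote a says that it need not. Sites will resolve this differently.

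What is at stake is the record of drug-exposed pregnancies. By setting a 14-day contraception window, the protocol treats conceptions up to that point as relevant. A conception late in treatment or in that window may not be recognised by a call on Day 14 to 21. Under the footnote it then need not be reported, and because only previously reported pregnancies are followed, it need not be followed to outcome either.

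**Working it through.** **1. Does footnote a conflict with Section 8.4.1?** No. The footnote omits a start time, and Section 8.4.1 supplies one: reduced reporting begins when the safety call is complete. Counting days from the last dose, full reporting runs from Day 0 to the call on Day 14 to 21, and the contraception window runs from Day 0 to at least Day 14. The exemption therefore starts 0 to 7 days after the minimum end of that window, not inside it.

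**2. Does it conflict with Section 8.4.5?** Yes, after the call. The participant is in the study, so the pregnancy occurs during the study. One text makes it reportable and the other removes the requirement.

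**3. Which exposed pregnancies fall in the gap?** Section 10.5.3 and the Schedule of Activities plan no pregnancy test after Visit 1. Testing follows a missed cycle, a suspicion or a local requirement, so timing depends on recognition.

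Let *c* be the day of conception relative to the last dose, *L* the recognition lag in days and *T* the day of the call. A pregnancy is first recognised after the call when *c* + *L* > *T*, that is, *c* > *T* − *L*. Taking conceptions up to Day 14, the band has length 14 − (*T* − *L*) = 14 + *L* − *T*. *T* is 14 or 21 (Section 8.10.6). *L* is assumed to be 14 to 42 days.

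| Lag *L* | Call *T* | Conceptions first known after the call | Length |
|---|---|---|---|
| 14 days | Day 21 | Day 7 to Day 14 | 14 + 14 − 21 = 7 days |
| 14 days | Day 14 | Day 0 to Day 14 | 14 + 14 − 14 = 14 days |
| 42 days | Day 21 | Day −21 to Day 14 | 14 + 42 − 21 = 35 days |
| 42 days | Day 14 | Day −28 to Day 14 | 14 + 42 − 14 = 42 days |

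The band is 7 to 42 days. With a 2-week lag it lies wholly after the last dose, within the contraception window. With a 6-week lag it also takes in the last 21 to 28 days of treatment.

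**4. Can this be turned into a count?** No. The documents give no pregnancy rate, no number of women of childbearing potential and no number who stop drug yet remain followed.

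**5. How does Appendix 7 compare?** Participants in the Durability Period are also off drug and past the safety call, yet their pregnancies are reportable. Early stoppers cannot enter that period, because its inclusion criteria require treatment through the evening before Visit 13. The Appendix 7 rule therefore never reaches them.

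**The case against.** The strongest reply is that the specific rule qualifies the general one: footnote a is the Table 3 content to which Section 8.4.1 points, and Section 8.4.5 should be read subject to it. Section 8.4.5 does not refer to Table 3 and states no exception, so a site cannot know this.

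Four further points carry some weight.

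- A pregnancy confirmed on drug itself requires discontinuation (Section 7.1), so it is known and reportable before the exemption starts. This stands.
- Adverse outcomes may still surface as serious events (Sections 8.4.5 and 10.3.2), and that row has no footnote. This stands in part: an exposed pregnancy with a normal outcome would not surface, and none would be registered before its outcome was known.
- Ordinary completers have the same recognition problem, since after follow-up Table 3 requires only that previously reported pregnancies be followed. This is true, but completers have left the study, whereas early stoppers are still being contacted within it.
- With a half-life of about 7 to 10 hours (Section 4.3.3), conceptions months after the last dose are of little interest. This is fair, and it is why a narrower fix is offered below.

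A reader might also infer that the footnote removes the 24-hour report of potential drug-induced liver injury in the days after drug is stopped. The documents do not support this. Such a case precedes the safety call, when Section 8.4.1 still requires full reporting. After the call, Section 8.4.7 defines ECIs as adverse events, and these remain reportable through their own rows. Only the ECI category and its timeframe lapse.

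**Conclusion.** The conflict with Section 8.4.5 is real, and footnote a also differs from the Appendix 7 rule. The practical gap is confined to women of childbearing potential who stop drug early, are still followed, and whose pregnancy was conceived on drug or by Day 14 but first recognised after the safety call. The affected conception band is about 7 to 42 days, resting on an assumed 2- to 6-week recognition lag and a call on Day 14 to 21.

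Two larger claims should not be drawn from this. Pregnancies conceived on drug or in the contraception window do not as a class go unreported: those known by the call are reportable and followed. Nor does the stated 20% dropout rate, 0.20 × 1290 = 258, measure the group at risk. It includes men, women not of childbearing potential, placebo participants and people who left the study, and it is a Week 24 rate. The number of affected pregnancies is likely small but cannot be estimated. This is a safety-reporting inconsistency with no bearing on efficacy, alpha or power.

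**What to change.** Reconcile footnote a with Section 8.4.5 by removing pregnancy/lactation exposure from the exemption, so that cases learned of while the participant is followed stay reportable within 24 hours. At a minimum, keep reportable any pregnancy learned of during that follow-up whose estimated conception falls on or before the end of the contraception window.

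For ECIs and overdose, repeat in the footnote the start time already given in Section 8.4.1: after completion of the safety follow-up call. This clarifies the rule without changing it.

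The cost is one footnote edit, a memo to sites and perhaps a few extra spontaneous reports. Under the full removal, some of these would concern conceptions long after exposure; the narrower wording avoids that but requires an estimated conception date. No visit or test is added.
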